Staff assessing outcome measures are blind to treatment arm, and for some measures receive training using videotaped and practice interviews until achieving high (ICC>.80) reliability based on 20 assessments by 2 raters. We achieve high inter-rater reliability (e.g., ICC>0.85 for PANSS total), and check for rater drift each 90d.

Specific Procedures: TCT is completed with a dedicated room and equipment. Staff trained with a UCSD-developed “TCT Clinician Competence Assessment” monitor TCT, clarify instructions and provide encouragement as needed. **In the initial “biomarker testing” session (Test 1),** subjects complete 1-h of Sound Sweeps to generate a “Pre-Training APS score” as described previously (Fig. 3) under identical circumstances and timelines as for the Test 2 session described below. Treatment group assignment (PBO vs. MEM) is then made using stratified random sampling (above) and 5-7 days later patients ingest either PBO (n=27) or 20 mg MEM (n=27) 240 min before completing the Sound Sweeps session (“Test 2”). MEM effects on APS learning are assessed both within-subject (APS (Test 1 - Test 2) for MEM group subjects: a key measure of **MEM sensitivity**) and between subjects (APS Test 2, PBO vs. MEM groups). After Test 2, all subjects are prescribed daily PBO or MEM using a standard titration schedule (MEM 5 mg at hs→ 5 mg bid→ 5 mg am/10 mg hs→ 10 mg bid over 3 weeks). Participants return to the laboratory to complete 1h TCT per our established procedures^{2,34}, which includes 5 modules of auditory/verbal processing exercises. Each module increases in difficulty as performance improves: **1) Sound Sweeps; 2) Syllable Identification:** Patients distinguish between 2 similar phonemes (e.g., “ba” vs. “da”), differing only in their voice onset time; **3) Word Matching:** Subjects match short similar-sounding consonant-vowel-consonant words (e.g., bad, dad); **4) Listen & Do:** Subjects reconstruct a spoken series of instructions and use a computer mouse to click icons on the screen in a specified order. This exercise is designed to stimulate verbal WM processes supported by the lateral PFC as well as premotor and motor processes. **5)**

Table 1. “Go” criteria: #1, plus at least one of #'s 2, 3 & 4 ($d>0.5$)

1. **Target engagement:** APS learning, MEM > PBO, p<0.05
2. **Greater** clinical, neurocognitive **or** functional gains:
 - ↓PANSSt, ↑MCCB-C **or** ↑Fnxn: MEM+TCT > PBO+TCT
3. **Faster** clinical, neurocognitive **or** functional gains:

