7. This approach might not work: Some evidence suggests that drug-enhanced APS learning, symptom reduction and neurocognitive gains from TCT may be dissociable, i.e. MEM might acutely enhance APS learning and EAIP biomarkers but have no impact on TCT-induced neurocognitive gains. Cain et al.⁹² reported that SZ patients taking the pro-extinction NMDA agonist, D-cycloserine (DCS) – but not those taking PBO - exhibited significant gains in APS learning and negative symptom reduction during an 8-week trial of TCT; DCS-enhanced APS learning was evident at the first time point (1 week). Interestingly, PBO- but not DCS-treated patients exhibited significant gains in MCCB performance. Thus, enhanced APS learning was associated with symptom reduction but not neurocognitive gains. This R33 application differs from the Cain et al.⁹² study in several specific ways, including: 1) this R33 uses a detailed conceptual framework for PACT design and implementation; 2) it benefits from previous dose/time optimization studies to maximize drug effects on APS learning; and 3) it uses a suite of hypothesis-driven biomarkers to identify potentially sensitive patient subgroups. Nonetheless, it is clear that MEM-enhanced TCT gains might be most evident in some but not all metrics (symptoms, neurocognition, function), even in the face of robust target engagement. With this awareness, we will carefully track and dissect these distinct outcome measures over the course of the R33, as we have in our published studies^{2,31,33,34,65,71}.

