8. Is this PACT “scalable”? This R33 design is optimized: a) patients are carefully characterized as part of a clinical trial; b) MEM dose and timing are optimized based on our previous studies; c) potential logistical hurdles that might cause subject attrition (transportation, food, reimbursement) are minimized; and d) biomarker assessment uses high fidelity lab-based measures that are not readily available in community-based settings for mental healthcare delivery. While this optimized design is feasible in our on-site laboratory (see below, “Feasibility”), a robust PACT design will face challenges in implementation in the “real world”. Importantly, we are studying different PACT delivery models, and are in discussions with a local Intensive Outpatient Program (IOP) (comparable to “Day Treatment”). The IOP model has been particularly successful in San Diego, and could be adapted to incorporate PACT into an integrated treatment, along with standardized biomarkers for personalized regimens, careful monitoring of clinical state and antipsychotic adherence, and individual and group supportive therapies. If this and a Confirmatory application support PACT efficacy, it will be “scalable.”

9. No control groups. Adding control “computer game” groups might reveal if PACT benefits reflect MEM use independent of TCT, computer use independent of TCT, and/or interactions of MEM+computer use. These are 3 very-low probability outcomes. We opted against this since: 1) efficacy of TCT is already known, so our primary aim is to assess the impact of added MEM vs. PBO; 2) recruitment demands for 4 groups will not yield “n’s” needed to detect meaningful Go/No-Go criteria; and 3) requiring patients to complete 30-h of non-therapeutic games for 10 weeks, or exposing patients to MEM under conditions that are unlikely to have lasting clinical value, is not ethically justified. Fisher et al.³⁷ found that patients randomized to computer game groups exhibited significant declines in verbal memory. Healthy subjects are not studied since no likely PACT effects on such subjects would alter the clinical implications of either positive or negative findings in SZ patients.

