4.2. Study Design

4.2.a. Narrative Study Description

Screened, eligible patients complete clinical, neurocognitive and functional measures and candidate biomarkers (EEG, QuickSIN, WIN). Aim 1 is completed in 2 tests, approximately 1 week apart. In Test 1, Sound Sweeps are tested after PBO for all subjects, who are then randomized to TCT+PBO vs. TCT+MEM arms (n=27/arm) using stratified random sampling (over sex, age and high/low Test 1 APS learning) blind to arm identity, similar to our previous studies. Test 2 follows approximately 5-7 d later; this test is identical to Test 1, except that subjects receive their assigned study drug (PBO vs. MEM (20 mg po) 1 hour prior to Sound Sweeps. Tests 1 and 2 are used to assess target engagement (Aim 1: MEM-enhanced APS learning) and MEM effects on auditory discrimination (QuickSIN, WIN). Our design allows for 20% attrition from enrollment (n=69) to completion of target engagement testing (n=54). For Aim 2, TCT in these same subjects is scheduled 3 d/week (M-W-F) for 1-h/d, recognizing the need for flexibility (T-Th are "make-up days"), and continues until a subject completes 30-h (approximately 10-12 weeks). TCT is delivered by trained staff. 60 min prior to each TCT session, patients take either PBO or 20 mg MEM, as per arm assignment. Patients and staff are blind to study arm; staff are blind to patients' baseline or post-intervention assessments. Outcome metrics assess symptom, neurocognitive and functional changes after 10, 20 and 30 TCT sessions, and 12 weeks post-TCT. Candidate biomarkers are re-tested after completion of 30 sessions of TCT.

4.2.b. Primary Purpose

Treatment

4.2.c. Interventions

Type	Name	Description
Behavioral (e.g., Psychotherapy, Lifestyle Counseling)	Targeted Cognitive Training (TCT)	Thirty, one-hour sessions over approximately 10 weeks, of computerized cognitive training modules.
Drug (including placebo)	memantine	The pro-cognitive medication, memantine (placebo vs. 20 mg) will be administered orally, 1 hour prior to targeted cognitive training, in a double-blind, randomized design.

4.2.d. Study Phase

Phase 2/3

Is this an NIH-defined Phase III Clinical Trial?

Yes No

4.2.e. Intervention Model

Parallel

4.2.f. Masking

Yes No

Participant Care Provider Investigator Outcomes Assessor

4.2.g. Allocation

Randomized

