4.4 Statistical Design & Power

Design (see “Research Strategy”, Figure 7): Screened, eligible patients complete clinical, neurocognitive and functional measures and candidate biomarkers. In Test 1, all subjects are tested in Sound Sweeps after PBO, and then assigned to TCT+PBO vs. TCT+MEM arms (n=27/arm) using stratified random sampling (over sex, age and high/low Test 1 (baseline) APS learning) blind to arm identity, similar to¹⁰⁷. Stratifying for baseline APS learning should increase the sensitivity of the primary target engagement metric. An example of a table for arm assignment is seen here:

Gender	Baseline	Age	Group								
Male	High	< 39	PBO	PBO	MEM	MEM	MEM	MEM	PBO	PBO	PBO
	High	≥ 39	PBO	MEM	PBO	MEM	MEM	PBO	MEM	PBO	PBO
	Low	< 39	MEM	MEM	PBO	PBO	PBO	PBO	MEM	MEM	MEM
	Low	≥ 39	MEM	PBO	MEM	PBO	PBO	MEM	PBO	MEM	MEM
Female	High	< 39	PBO	PBO	MEM	MEM	MEM	MEM	PBO	PBO	PBO
	High	≥ 39	PBO	MEM	PBO	MEM	MEM	PBO	MEM	PBO	PBO
	Low	< 39	MEM	PBO	MEM	PBO	PBO	MEM	PBO	MEM	MEM
	Low	≥ 39	MEM	MEM	PBO	PBO	PBO	PBO	MEM	MEM	MEM

Example of table for stratified random sampling, by gender, baseline APS learning (post-PBO) and age (based on approximate mean age (39 yo) of last 100 SZ patients tested in our program)

Test 2 follows approximately 5-7 days later. Tests 1 and 2 are used to assess target engagement (Aim 1: MEM-enhanced APS learning) and MEM effects on auditory discrimination. Our design allows for 20% attrition from enrollment (n=69) to completion of target engagement testing (n=54).

For Aim 2, TCT is scheduled 3 d/week and continues until a subject completes 30-h (approximately 10-12 weeks). 60 min prior to each TCT session, patients take either PBO or 20 mg MEM, as per arm assignment. Patients and staff are blind to study arm; staff are blind to patients’ baseline or post-intervention assessments. Outcome measures are assessed after sessions 10, 20 and 30, and 12 weeks post-TCT. See “Research Strategy” for details.

General Statistical Approach: Hypothesis tests are 2-sided ($\alpha=.05$). Type I error is controlled by selecting optimal *a priori* targets for primary analyses; secondary analyses use false discovery rate corrections. When appropriate, missing data are handled via multiple imputation or full information maximum likelihood estimation. Expected drop-out rates and ways to minimize them are described in the parent application.

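### Section 4 gives the Aim 2 drug as a pre-session dose, against the Research Strategy's daily titrated regimen, and the Test 2 dose-to-test interval has two conflicting values

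*Combined protocol and SAP*

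**What the plan says.** **Training phase (Aim 2).** Section 4.2.a and Section 4.4 both say: "60 min prior to each TCT session, patients take either PBO or 20 mg MEM, as per arm assignment". The Interventions table in 4.2.c says that memantine or placebo "will be administered orally, 1 hour prior to targeted cognitive training, in a double-blind, randomized design". None of the three mentions daily dosing, titration or a taper.

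The Research Strategy describes a different regimen. Its Design paragraph has everyone titrated to 20 mg over three weeks while training begins. Specific Procedures prescribes daily drug in steps of 5, 10, 15 and 20 mg per day, ending at 10 mg twice a day. The Post-treatment protocol adds a three-week taper for those who stop. The Abstract, the Specific Aims and items 4 and 5 of the numbered questions also describe daily use.

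**Test 2 dose (Aim 1).** Specific Procedures says "patients ingest either PBO (n=27) or 20 mg MEM (n=27) 240 min before completing the Sound Sweeps session". Section 4.2.a says "subjects receive their assigned study drug (PBO vs. MEM (20 mg po) 1 hour prior to Sound Sweeps". Test 1 is run "under identical circumstances and timelines as for the Test 2 session described below", and 4.2.a adds that "In Test 1, Sound Sweeps are tested after PBO for all subjects". Items 7 and 8 rely on earlier timing work ("it benefits from previous dose/time optimization studies to maximize drug effects on APS learning"; "MEM dose and timing are optimized based on our previous studies") but give no interval.

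**The concern.** A protocol should give one drug regimen and one dosing time for its key test. Here, a reader who takes the Aim 2 regimen from the synopsis, whether for a pharmacy instruction or for the report of the trial, would write down three 20 mg doses a week instead of a titrated twice-daily schedule. Item 4 justifies the treatment-phase dose by the known safety and tolerability of 20 mg daily in divided doses. The schedule in Section 4 is not the one that this argument covers.

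The Test 2 interval matters for a separate reason. Target engagement at p<0.05 is required for any Go decision (Table 1). The change from Test 1 to Test 2 in memantine patients is also the plan's measure of individual memantine sensitivity, which is later used as a predictor of outcome. The time from dose to test sets the memantine exposure behind both.

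**Working it through.** **1. Can the two Aim 2 descriptions be combined?** No. A 20 mg pre-session dose contradicts the 5, 10 and 15 mg/day titration steps, and it contradicts a 20 mg daily total split into two 10 mg doses.

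**2. Which one is intended?** Three things point to the Research Strategy.
- The design text of 4.4 that contains the 60-minute wording ends by sending the reader to the Research Strategy for detail.
- Item 5 contrasts the two drugs directly: staff give amphetamine before each session, while memantine is part of the patient's daily regimen.
- Section 4.4 carries signs of text taken from another application. It garbles the drug name as 5 mg MEMetamine where the Research Strategy's power paragraph has 20 mg MEM. It cites Fig. 3A where that paragraph cites Fig. 3. It also points to a Figure 7, although the design figure here is Fig. 5. These slips are clerical and count only as evidence of carry-over.

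**3. Size of the Aim 2 difference.**
- Section 4: 3 sessions × 20 mg = 60 mg/week.
- Research Strategy at full dose: 7 days × 20 mg = 140 mg/week.
- Ratio: 60/140 = 43%. This needs no assumption about titration.

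For the whole course the length of each titration step is not stated, so the totals are an illustration only:
- Section 4: 30 × 20 = 600 mg.
- Research Strategy, lower end (one week per step; 65 days, the programme's own mean for 30 sessions): 7 × (5 + 10 + 15) + 44 × 20 = 210 + 880 = 1,090 mg.
- Research Strategy, upper end (four equal steps over 21 days; 12 weeks): 21 × 12.5 + 63 × 20 = 262.5 + 1,260 = 1,522.5 mg.
- Ratio: 600/1,522.5 = 39% to 600/1,090 = 55%.

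**4. Test 2 interval.**
- 4.2.a: 60 min before Sound Sweeps.
- Specific Procedures: 240 min before the session is completed. If the session is only the one-hour exercise, the dose falls 240 − 60 = 180 min before the start, three times the 4.2.a figure. If the 240 min was meant to run to the start, the ratio is four.

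The two values agree only if the session means a longer visit. Sound Sweeps would have to begin 60 min after the dose and the visit end at 240 min, which leaves 180 min. The exercise takes 60 min and one EEG recording takes 25 + 6 = 31 min. The remaining 180 − 60 − 31 = 89 min would have to go to the speech-in-noise, cognitive and other measures, whose durations are not given. The documents neither state nor exclude this.

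**5. Does any statistical figure depend on this?** No. The stated n=27 per arm uses d=0.5, 80% power, two-sided alpha 0.05 and a test-retest correlation of 0.8. The SD of the change score is √(2(1 − 0.8)) = 0.632. The normal approximation gives 26 per arm, and 27 per arm gives 81% power by the noncentral t, so the figure reproduces. Dosing time is not an input.

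**The case against.** The strongest reply is that the Aim 2 regimen is not in doubt. Section 4 is headed as a synopsis, 4.4 defers to the Research Strategy, and item 5 says outright that memantine is taken daily. Staff working from Specific Procedures would dose as intended. This stands: it makes the first part a correction of stale text and rules out reading the regimen as undecided.

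A reader might infer four stronger things, none of which the documents support.
- **Item 13 shows that the two regimens act differently.** It contrasts one dose with several. Thirty pre-session doses and daily dosing are both multiple-dose regimens, so it does not separate them.
- **Section 4 would leave patients drug-free between sessions.** They would have days without a dose, but the documents give no half-life, so absence of drug is not shown.
- **The two Test 2 intervals cannot be reconciled at all.** Specific Procedures measures to completion of the session and labels that session Test 2, a visit that also includes EEG, auditory and cognitive measures. The longer-visit reading is strained but not impossible, so 180 min is not a proven lower bound.
- **The Aim 1 comparison is biased.** Placebo and memantine patients would follow the same interval, so the randomised contrast is valid under either value. Only the exposure being tested would differ.

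**Conclusion.** The point holds and should be corrected. Section 4 is wrong as written on the Aim 2 drug: 60 against 140 mg per week at full dose, with daily dosing and titration left out. The intended regimen can be recovered from the Research Strategy. That the wrong text was carried over from an amphetamine application is a well-supported inference; the contradiction itself is plain.

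The Test 2 interval is the open question. On the plain reading it is 60 min in one place and about 180 min or more to the start of the exercise in another. The second figure assumes that the session is only the one-hour exercise. The documents do not say which value is right, nor how far the Aim 1 effect would change between them. Randomisation, blinding, sample size and the planned models are untouched.

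**What to change.** 1. Amend 4.2.a, the 4.2.c table and 4.4 to the regimen in the Design and Specific Procedures paragraphs: daily drug, titrated over three weeks to 10 mg twice a day. Delete the 60-minute and 1-hour pre-session wording.
2. Ask the sponsor to confirm one Test 2 interval from its time-course data, measured from dose to the start of Sound Sweeps. State it identically in Specific Procedures and 4.2.a, with the same timeline for the Test 1 placebo. Do not write in 240 min to the start by default, because Specific Procedures measures 240 min to completion.

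The cost is text edits in four places and one check of data the sponsor already holds. No patients, procedures or analyses are added. The clerical slips in 4.4 can be corrected in the same edit, but the point does not depend on them.

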4.3. Outcome Measures

Type	Name	Time Frame	Brief Description
Primary	Auditory Processing Speed (APS) learning	Test 1 and Test 2, one week apart	APS is measured before and after the TCT "Sound Sweeps" frequency modulation session, to determine the amount of "learning", based on the reduction in detection gap (ms). More learning (greater gain in processing speed) with memantine vs. placebo confirms target engagement, which is the primary outcome of Aim 1.
Primary	MCCB Composite	baseline vs. post-TCT session 10, 20 and 30 (approximately 10 weeks), and 12 weeks post-TCT	Change in MCCB Composite performance from baseline is one outcome measure. The MCCB measures 7 cognitive domains: speed of processing, attention/vigilance, working memory (verbal and nonverbal), verbal learning, visual learning, reasoning/ problem solving and social cognition. Details are found in[25, 89, 90]; past studies of drug effects on MCCB performance include[37, 91]. Since the MCCB is assessed multiple times, alternate forms of the HVLT-R and BVMT-R are used in counterbalanced order. MCCB Global Composite T-score (MCCB-C) is the primary neurocognitive outcome measure. Individual MCCB domain T-scores are used in secondary analyses to determine whether an overall effect is driven by specific aspects of neurocognition; TCT effects on verbal learning performance are known to be robust[13], and should be augmented by MEM. Baseline and MEM-enhanced (Test 2 vs. 1) MCCB performance (A/V subscale) will also be tested as potential biomarkers/moderators of MEM PACT efficacy.
Primary	PANSS: Positive & Negative Symptom Scale total	baseline vs. post-TCT session 10, 20 and 30 (approximately 10 weeks), and 12 weeks post-TCT	TCT reduces both positive and negative symptoms of psychosis; we predict that memantine will augment these effects via enhanced TCT learning, detected by the PANSS. For this reason, and based on the need to limit total outcome measures, PANSS Total Score is the primary clinical outcome measure. Positive and negative symptom subscales, as well as PANSS factor-derived measures, will be assessed in exploratory analyses. Other secondary clinical measures will include: 1) Psychotic Symptom Rating Scales (assesses auditory hallucinations); 2) Young Mania Rating Scale; 3) Patient Health Questionnaire-9 (current depressive symptoms); 4) Abnormal Involuntary Movement Scale; 5) Columbia Suicide Severity Rating (C-SSRS); "Lifetime/Recent version" at screen; "Since Last Visit" at follow-up visits). The C-SSRS is a sensitive measure of suicidal ideation; any "yes" in C-SSRS prompts an immediate full evaluation/ action plan by a study M.D.

Primary	World Health Organization Disability Schedule 2.0 (WHODAS)	baseline, after sessions 10, 20 and 30, and 12 weeks post-TCT	Function is assessed via the World Health Organization Disability Schedule 2.0 (WHODAS) at baseline, after sessions 10, 20 and 30, and week 12 post-TCT. WHODAS 2.0 is a 12-item patient-rated measure (< 15 min) using a 5-point Likert scale focusing on cognition, mobility, self-care, getting along with people, life activities and participating in society; it was selected by the DSM-5 Task Force committee to replace the global assessment of functioning scale. NIH "PhenX Toolkit" scales of Impairment, QOL and Social Isolation will also be used. After session #30, the assessment will include a 14-item 7-point Likert scale of treatment satisfaction.
Primary	EEG biomarkers	baseline, visit 2 and after session 30	Biomarkers from Tests 1-2 will be assessed as predictors of target engagement (Aim 1) and PACT sensitivity (Aim 2). EEG measures of early auditory information processing variably predict response to early APS learning[74], MEM-enhanced APS learning[62], and TCT outcomes[18]. EEG/ERPs are acquired via 64-channel recording systems and assessed in the same order, as per[38, 94]: MMN/P3a/Theta power/Phase locking (25 min; Oddball Paradigm), ASSR (6 min). Exploratory analyses will test secondary predictions: for example, high vs. low baseline P3a amplitude and faster P3a latency will predict greater target engagement (Aim 1), and greater MEM-enhanced TCT outcome (Aim 2). MEM-enhanced (Test 2 vs. 1) ERPs, auditory discrimination and neurocognitive (A/V) measures will also be explored as outcome (Aim 2) predictors; significant pre- vs. post-TCT changes in ERP source dynamics will also be examined for mechanistic characterization[20]. Robust biomarker predictors will be examined as moderator

